8.14.3. Grading and Severity

Grade refers to the severity of the AE/SAE. Severity will be assessed in this study using the NCI CTCAE, version 4.03 (see Section 12.2.1).

In the event that an AE is not covered by the CTCAE, the assessment of severity will be determined by using the CTCAE general guideline:

Table 8: Grading for Events Not Covered By the CTCAE

Grade 1	Mild; asymptomatic or mild symptoms; clinical or diagnostic observations only; intervention not indicated.
Grade 2	Moderate; minimal, local or noninvasive intervention indicated; limiting age-appropriate instrumental ADL*.
Grade 3	Severe or medically significant but not immediately life-threatening; hospitalization or prolongation of hospitalization indicated; disabling; limiting self-care ADL**.
Grade 4	Life-threatening consequences; urgent intervention indicated.
Grade 5	Death related to AE
Activities of Daily Living (ADL)	
*Instrumental ADL refer to preparing meals, shopping for groceries or clothes, using the telephone, managing money, etc.	
**Self-care ADL refer to bathing, dressing and undressing, feeding self, using the toilet, taking medications, and not bedridden.	

The Investigator will evaluate all AEs as to their severity.

- An AE that is assessed as severe should not be confused with an SAE. Severity is a category used for rating the intensity of an event; both AEs and SAEs can be assessed as severe. An event is described as 'serious' when it meets one of the pre-defined outcomes as described in Section 8.14.5

Worsening of a pre-treatment event, after initiation of JTX-2011 alone or in combination with nivolumab, ipilimumab or pembrolizumab must be recorded as a new AE.

8.14.4. Relationship Categorization

An Investigator qualified in medicine must make the determination of relationship to study drug for each AE/SAE. The Investigator should decide whether, in his or her medical judgment there is a reasonable possibility that the event may have been caused by the study drug. If no valid reason exists for suggesting a relationship, the AE/SAE should be classified as "definitely not". If there is a valid reason, even if undetermined or untested, for suspecting a possible cause-and-effect relationship between the study drug and the occurrence of the AE/SAE, the AE/SAE

should be considered “possibly related”. Table 9 should be used for guidance in the determination of relationship:

Table 9: Guidance in Determining the Relationship of an Adverse Event

Term	Relationship	Definition
Unrelated	No	There is no association between study drug and the reported event.
Possible	Yes	The event follows a reasonable temporal sequence from the time of study drug administration and/or follows a known response pattern to the study drug, but could also have been produced by other factors.
Probably Related	Yes	A definite causal relationship exists between study drug administration and the AE, and other conditions (concurrent illness, progression/expression of disease state, or concurrent medication reaction) do not appear to explain the event.

If the causal relationship between an AE/SAE and JTX-2011 alone or in combination with nivolumab, ipilimumab, or pembrolizumab is determined to be possible or related, the event will be considered to be related to JTX-2011 for the purposes of expedited regulatory reporting.

8.14.5. Outcome Categorization

Outcome of an AE/SAE may be classified as resolved, resolved with sequelae, unresolved, or fatal. Death is an outcome of an event. The event that resulted in death must be recorded on the appropriate CRF.

8.14.6. Clinical Laboratory Evaluations

A clinical laboratory AE is any laboratory value that is considered clinically significant by the Investigator and has caused a medical intervention or accompanied by clinical symptoms. Laboratory abnormalities that have not required medical intervention should not be recorded as AEs and will be captured and reported in the Laboratory section of the clinical study report. If a medical intervention occurs, it should be recorded as a treatment with the abnormal laboratory finding as the AE.

The Investigator should decide, based upon the AE criteria and the clinical condition of the patient, whether a change in a laboratory parameter is clinically significant and therefore represents an AE.

8.15. Pregnancy

Pregnancy will not be considered a serious adverse event. [REDACTED]

If the outcome of the pregnancy meets serious criteria (miscarriage or congenital anomaly/birth defect), it should be reported as an SAE.

The pregnant female study participant must be withdrawn from the study. Every effort should be made to gather information regarding the pregnancy outcome until 8 weeks post-partum. It is the responsibility of the Investigator to obtain all pregnancy information.

8.16. Serious Adverse Event Reporting

8.16.1. Definition of a Serious Adverse Event (SAE)

A Serious Adverse Event is any untoward medical occurrence (whether considered to be related to study drug or not, except for those events described in Section 8.16.3) that at any dose:

- Results in death;
- Is life-threatening (the term “life-threatening” in the definition of “serious” refers to an event which the patient was at risk of death at the time of the event; it does not refer to an event which hypothetically might have caused death if it were more severe);
- Requires inpatient hospitalization (at least 24 hours inpatient) or prolongation of existing hospitalization;
- Results in persistent or significant disability/incapacity;
- Is a congenital abnormality/birth defect.

Medical and scientific judgment should be exercised in deciding whether expedited reporting is appropriate in other situations, such as important medical events that may not be immediately life-threatening or result in death or hospitalization but may jeopardize the patient or may require intervention to prevent one of the other outcomes listed in the definition above as these events may be considered serious.

Examples of such events are intensive treatment in an emergency room or at home for allergic bronchospasm; blood dyscrasias or convulsions that do not result in hospitalization.

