8.14.1. Definition of an Adverse Event (AE)

An AE is any untoward medical occurrence in a clinical investigation subject administered a pharmaceutical product and which does not necessarily have to have a causal relationship with this treatment.

An AE can therefore be any unfavorable and unintended sign (including clinically significant abnormal laboratory finding), symptom, disease, or exacerbation of a pre-existing condition temporally associated with the use of study drug, whether or not related to the study drug.

Disease progression should not be recorded as an AE/SAE. New or increasing symptoms related to disease progression should be reported as an AE or AEs. When possible, the primary diagnosis of the event meeting SAE criteria should be recorded as the AE/SAE term. (For instance, if a patient is hospitalized for shortness of breath and it is confirmed that this is a symptom of a malignant pleural effusion, then malignant pleural effusion should be reported as the event term, rather than disease progression).

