8.16.3. Protocol-Specified Expected Events

Patients with advanced solid malignancies are at risk for many adverse events as a consequence of prior therapy and as a result of their disease.

Subjects receiving immune therapies are at risk for immune-related AEs. IrAEs are typically responsive to interruption or discontinuation of the immunotherapy in combination with immunosuppressive drugs such as steroids or occasionally tumor necrosis factor-blocking antibodies. At present, there is no clear preventive strategy to avoid irAEs {Michot 2016}.

These events that are expected due to the subject’s disease or “immune-related” events that are expected with immunostimulatory therapy must be reported in the clinical database:

- Disease-related adverse events may include:

- Fatigue;
- Bone, joint, or muscle pain;
- Disease progression;
- Death due to disease progression;
- Cough in subjects with lung cancer;
- Dysphagia or odynophagia in subjects with head and neck cancer;
- Abdominal pain in subjects with gastric cancer.
- General therapy-related events may include:
 - Catheter-related events.
- Immune-related adverse events (well documented and expected with nivolumab, ipilimumab, and pembrolizumab, and expected with JTX-2011) may include:
 - Dermatitis;
 - Pneumonitis;
 - Hepatitis;
 - Enterocolitis;
 - Hypophysitis;
 - Adrenal insufficiency;
 - Thyroid dysfunction;
 - Nephritis;
 - Infusion reaction;
 - Rash;
 - Pruritus;
 - Vitiligo.

The occurrence of these expected events will be monitored by Jounce and may be submitted to health authorities in either an expedited or non-expedited manner, as appropriate.

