8.16.4. Observation and Recording of SAEs

All SAEs must be reported to Novella within 24 hours of first awareness of the event.

Additional follow-up information, if required, or available, should be recorded on a follow-up SAE Report Form and faxed to Novella Drug Safety within one business day of discovery by site.

All SAEs, whether related or unrelated to study drug, will be recorded from the time of signed informed consent until resolution or new therapy initiated or for 28 days post final dose if no new therapy is initiated. Any SAEs considered to have at least a possible relationship to the study drug and discovered by the Investigator at any time period after the subject's study treatment has ended should be reported according to the timeframe described above.

Study drug-related SAEs will be followed until resolution, stabilization or subject receives new therapy.

At a minimum, the site number, Investigator's name, subject number, event name, the date of onset, a short description of the event and the Investigator's preliminary assessment of causality must be provided at the time of the initial SAE report.

The onset date of the SAE is defined as the onset date of signs and symptoms or a change in baseline when the SAE met seriousness criteria.

The resolution date of the SAE is defined as the date in which the criteria of seriousness is no longer applicable (e.g., discharge from hospitalization).

All SAEs that are ongoing events at the time of death should be considered not resolved at time of death.

The Investigator is encouraged to discuss with the Medical Monitor any SAEs for which the issue of reportability is unclear or in question.

The Investigator must review, sign, and date the SAE Report Form to confirm the accuracy of the information recorded on the SAE Report Form along with the corresponding source documentation.

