## **8. ENDPOINT DEFINITIONS AND DERIVATIONS**

### **8.1 SAFETY DEFINITIONS AND ENDPOINTS**

#### **8.1.1 ADVERSE EVENT ENDPOINTS**

Adverse events will be categorized by pre-existing, treatment emergent and post treatment.

- Pre-existing AEs are designated to events that occur prior to the first dose of study drug(s) or observed prior to first dose but did not increase in NCI CTCAE toxicity grade during treatment period.
- Post-treatment adverse events will be any adverse events reported outside the 28 day post dose treatment window until the end of study participation. Any subsequent non-protocol treatment for the cancer diagnosis will end the potential study drug(s) adverse event data collection.
- Treatment-Emergent Adverse Events (TEAEs) are designated to events that occur after the start of study drug(s) and on or before 28 days after final dose of study drug, and were not observed prior to start of treatment; Or if the event was observed prior to the start of study drug but increased in NCI CTCAE grade after either the start of study drug or prior to 28 days after the final dose of study drug. Pre-existing adverse events may be reclassified as TEAEs if the frequency of the event increases during treatment.
- Treatment Related TEAEs will include those TEAEs which are possibly or probably related to study drug(s) as designated by the investigator. Events having a missing relatedness will be designated as definitely related on tables but the listing will display the data as collected. Relationship may be attributed by JTX-2011 and/or nivolumab/ipilimumab/pembrolizumab and will be displayed separately.
- Serious adverse events (SAEs) will include all events classified as serious on the eCRF. The electronic database used to enter data at the site (i.e., RAVE / iMedidata) will be deemed as the complete report for adverse event information. The pharmacovigilance database will be reconciled against the EDC.

- Infusion related reactions (IRRs) may be captured as an adverse event as well as the symptoms that cause the IRR. Symptoms of IRRs are events occurring shortly after or during the study drug infusion. Symptoms may include but are not limited to: flushing, headache, nausea, fever, chills, dyspnea, rash, hypotension, wheezing, coughing, tachycardia. Any sign/symptom determined to be associated with an IRR may be counted as such in adverse event reporting. The highest grade sign/symptom must be associated with the IRR preferred term.

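### Read literally, the SAE definition in Protocol 8.16.1 excludes the immune-related toxicities listed in 8.16.3, even when they are fatal or lead to hospitalization

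*Protocol*

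**What the plan says.** Protocol 8.16.1 calls an untoward occurrence serious when it meets a listed criterion, the first being "Results in death", and it carves out the events of 8.16.3: "except for those events described in Section 8.16.3) that at any dose".

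Section 8.16.3 has three groups: disease-related events, catheter-related events, and immune-related events. The third is introduced with "Immune-related adverse events (well documented and expected with nivolumab, ipilimumab, and pembrolizumab, and expected with JTX-2011) may include". For the disease-related and immune-related events the stated duty is that "events that are expected with immunostimulatory therapy must be reported in the clinical database"; submission to health authorities is left open as to whether and how fast.

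The fast reporting duty is in 8.16.4: "All SAEs must be reported to Novella within 24 hours of first awareness of the event". It is attached to SAEs and to nothing else.

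On progression, Protocol 8.14.1 states: "Disease progression should not be recorded as an AE/SAE".

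The SAP adds no seriousness rule of its own. SAP 8.1.1 says: "Serious adverse events (SAEs) will include all events classified as serious on the eCRF".

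**The concern.** Whether an event is serious depends on its outcome. Whether it is expected depends on what is already known about the drug, and bears on how quickly the sponsor must tell authorities. Section 8.16.1 uses a list of expected events to decide seriousness, so the two attributes are merged. The events caught are not marginal. They are the toxicities these drugs are anticipated to cause, and several of them (colitis, pneumonitis, hepatitis, hypophysitis, adrenal insufficiency, nephritis, rash) have their own rows in Protocol Table 5.

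This is a first-in-human trial with safety and tolerability among the primary objectives of every part. At stake are the 24-hour notification of serious drug toxicity and the meaning of the SAE tables in the study report. If some sites apply the exception and others disregard it, the same clinical event is flagged serious at one site and not at another. The progression conflict raises a similar problem for deaths: whether a progression death appears as an adverse event with a fatal outcome could depend on which section the site followed.

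**Working it through.** No arithmetic decides this point. The check sets the sections against each other.

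1. **What the exception covers.** Section 8.16.3 names 7 disease-related items, 1 therapy-related item (catheter events) and 12 immune-related items: dermatitis, pneumonitis, hepatitis, enterocolitis, hypophysitis, adrenal insufficiency, thyroid dysfunction, nephritis, infusion reaction, rash, pruritus and vitiligo. That makes 7 + 1 + 12 = 20 named items. None of the 12 is limited by grade, outcome or causality, and the list is worded as open-ended.

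2. **Applying the definition.** A fatal pneumonitis meets the death criterion in 8.16.1. Pneumonitis is described in 8.16.3. The exception therefore removes it. The same steps apply to each of the other 11 immune-related items, and to hospitalization in place of death.

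3. **Consequence for reporting.** Section 8.16.4 requires 24-hour reports of SAEs. An event outside the definition does not trigger it. Section 8.16.3 supplies database entry but no time limit.

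4. **Is SAE status restored elsewhere?**
   - Protocol 8.14.2 sends the reader to 8.16 for the SAE definition, so 8.16.1 governs.
   - Protocol 8.14.3 describes seriousness by outcome, with no exception. It cites 8.14.5, which only classifies how an event ended, instead of 8.16.1.
   - Protocol 8.17 asks the investigator to notify the IRB of events that are serious, related and unexpected. That treats seriousness and expectedness as separate attributes.
   - No section says that a listed event becomes an SAE once it meets a seriousness criterion.

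   Sections 8.14.3 and 8.17 therefore conflict with 8.16.1 without overriding it.

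5. **After the End of Treatment visit.** General AE recording stops at that visit, 28 ± 7 days after the last dose (8.14.2). Later events enter explicitly only as possibly related SAEs (8.16.4). Protocol 1.6.3 warns that ipilimumab immune reactions can be fatal and can appear weeks to months after stopping. On the literal text a late listed event has no clearly defined route: it falls outside the AE window, it is not an SAE, and 8.16.3 gives no window of its own.

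6. **Consequence for analysis.** SAP 8.1.1 takes seriousness from the eCRF, and SAP 9.9.1 with Table 7 builds on that.

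| Depends on the serious flag | Does not depend on it |
|---|---|
| Serious TEAE tables | TEAE tables by SOC, PT and maximum grade |
| Related SAE tables | Immune-related AE and infusion-reaction tables |
| SAE listing and the SAE line of the overview table | TEAEs resulting in death, in dose interruption, reduction or hold, or in discontinuation |
| | DLT summaries |

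   The reconciliation of the pharmacovigilance database with EDC (SAP 8.1.1) would not reveal an event that the site treated as non-serious in both, because the two sources would agree.

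7. **Progression.** Section 8.16.3 lists disease progression and death due to it among the disease-related adverse events that must go into the database. Section 8.14.1 says progression is not to be recorded as an AE or SAE. Both cannot be followed.

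**The case against.** The literal reading is not the only possible one. The exception sits inside the parenthesis on causality: "whether considered to be related to study drug or not, except for those events described in Section 8.16.3) that at any dose". It could be taken to qualify only that clause. The heading of 8.16.3 speaks of expected events, and its closing sentence contemplates expedited submission, which 8.17 links to SAEs; that suggests the authors thought listed events could be serious. The rules for drug-related SAEs in 7.5 and 8.16.4 would also have little to act on if the main anticipated toxicities were excluded. All of this is fair as evidence of intent. It shows that the protocol conflicts with itself; it does not repair the definition that sites are directed to use.

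A second objection does stand and limits the consequence. The listed events remain AEs, must be entered in the database and are monitored by the sponsor. Section 8.14.5 requires the event that caused a death to be recorded. An on-treatment fatal pneumonitis should therefore still appear in the immune-related, maximum-grade and death outputs.

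Three stronger inferences are tempting and are not supported:

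- **That the Safety Monitoring Committee loses 24-hour reports.** Section 8.16.4 sends those reports to the safety contact only. The committee reviews AEs and SAEs before escalation decisions (6.1.1) and then about every 3 months (6.1.2), and listed events remain AEs within that review.
- **That the Related SAE rate is understated by the share of serious events in the listed categories, and that this share is large.** This assumes every site applies the exception. It also treats a share of events as a share of subjects, although the tables count a patient once per SOC or PT, and no document gives the share.
- **That sites did in fact report differently.** The SAE form and the eCRF completion instructions are not among the documents, so this is a possibility only.

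**Conclusion.** The point holds as an internal contradiction with a specific consequence. On the plain wording, 12 immune-related categories are outside the SAE definition whatever their grade or outcome, and the 24-hour duty does not reach them. The analyses at risk are limited to those using the serious flag. The numerical effect is unknown: it depends on how sites read 8.16.1 and on how many serious events fall in the listed categories, and neither is documented. It could be nil if every site disregarded the exception. The disease-progression conflict between 8.14.1 and 8.16.3 is separate and smaller.

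Correction is still warranted before the SAE tables are relied on, because the defect concerns the reporting of serious drug toxicity and is cheap to remove.

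**What to change.** 1. In 8.16.1, delete the exception, or restrict it to disease progression and death due to disease progression, in line with 8.14.1.
2. In 8.16.3, state that listing an event affects its expectedness only, and that a listed immune-related or therapy-related event meeting a seriousness criterion is an SAE under 8.16.4.
3. Reconcile 8.16.3 with 8.14.1 so that progression and progression deaths are handled one way.
4. In 8.14.3, correct the cross-reference so that it points to 8.16.1.
5. Before database lock, query every AE in the listed categories that has a fatal outcome or led to hospitalization and is not flagged serious. The fatal outcome is a recorded category under 8.14.5; whether hospitalization can be found without the serious flag depends on the eCRF, which the documents do not show. Where dosing in a part is already complete, this query does most of the correcting.

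The cost is a short wording amendment and one query listing. The downside is some additional 24-hour reports and a higher reported SAE count.

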8.16.2. SAE Classifications

Elective or previously scheduled hospitalizations for pre-existing conditions which have not worsened after initiation of treatment should not be classified as SAEs. For example, an admission for a previously scheduled ventral hernia repair would not be classified as an SAE.

8.16.3. Protocol-Specified Expected Events

Patients with advanced solid malignancies are at risk for many adverse events as a consequence of prior therapy and as a result of their disease.

Subjects receiving immune therapies are at risk for immune-related AEs. IrAEs are typically responsive to interruption or discontinuation of the immunotherapy in combination with immunosuppressive drugs such as steroids or occasionally tumor necrosis factor-blocking antibodies. At present, there is no clear preventive strategy to avoid irAEs {Michot 2016}.

These events that are expected due to the subject’s disease or “immune-related” events that are expected with immunostimulatory therapy must be reported in the clinical database:

- Disease-related adverse events may include:

- Fatigue;
- Bone, joint, or muscle pain;
- Disease progression;
- Death due to disease progression;
- Cough in subjects with lung cancer;
- Dysphagia or odynophagia in subjects with head and neck cancer;
- Abdominal pain in subjects with gastric cancer.
- General therapy-related events may include:
 - Catheter-related events.
- Immune-related adverse events (well documented and expected with nivolumab, ipilimumab, and pembrolizumab, and expected with JTX-2011) may include:
 - Dermatitis;
 - Pneumonitis;
 - Hepatitis;
 - Enterocolitis;
 - Hypophysitis;
 - Adrenal insufficiency;
 - Thyroid dysfunction;
 - Nephritis;
 - Infusion reaction;
 - Rash;
 - Pruritus;
 - Vitiligo.

The occurrence of these expected events will be monitored by Jounce and may be submitted to health authorities in either an expedited or non-expedited manner, as appropriate.

